3.2.2 Blinding

Treatment assignment for all subjects enrolled in this study will be double-blind; the subject, all site personnel, and Clinical Research Organization (CRO) personnel (with the exception of the Medical Monitor providing safety oversight) involved in this study will not know the treatment given to any subject. Every effort should be made to maintain the study blind.

3.2.3 Dosing Schedule

The study medication is for external use only and will be administered at the clinic by the subject under the supervision of trained site personnel. Wearing gloves, supplied by the clinic staff, a single dose of the assigned treatment will be topically applied to each knee on each of four dosing days. Both knees will be treated for all subjects, if possible, however only one knee will be the

study knee on which assessments are performed. The first application of medication will be at Visit 2 on Day 1 (initiated at Time 0). Dosing on each of the three subsequent treatment days should be performed at the same time of day ± 2 hours in relation to the start time of the initial dose on Day 1.

3.2.4 Subject Compliance

Subjects will be free to withdraw from treatment or from the study at any time for any reason, or they may be withdrawn/removed, if necessary (see reasons for withdrawal below). It is understood by all concerned that an excessive rate of withdrawals can render the study uninterpretable; therefore, unnecessary withdrawal of subjects should be avoided.

Subjects will be removed from treatment for the following reasons:

- Unacceptable acute toxicities defined as:
 - Occurrence of a Dose-limiting toxicity (DLT)

Subjects will be removed from the study for the following reasons:

- Withdrawal of consent
- Non-compliance/Lost to follow-up
- Pregnancy

If treatment with study drug is interrupted and permanently stopped, subjects should remain on study and will be followed for scheduled safety and study assessments through Day 35. If the subject goes onto other treatment, this should be noted in the source documents and the concomitant medications electronic case report form (eCRF).

4. GENERAL CONSIDERATIONS FOR DATA ANALYSIS

Unless otherwise specified, continuous variables will be summarized using descriptive statistics (n, mean, standard deviation, median, minimum, and maximum). Categorical variables will be summarized showing the number and percentage of subjects within each category.

Summary results will be provided for each treatment group. All tabulations will be based on pooled data across centers.

All efficacy and tolerability statistical tests will be two-sided and tested at the 5% level of significance.

Analyses will be performed using SAS for Windows statistical software, version 9.4 or higher (SAS, Cary, NC), except where other software may be deemed more appropriate.

CTI will perform all efficacy and safety final analyses described in this SAP.

Subject data will be listed, sorted by treatment group and subject number.

4.1 Data Quality Assurance

The study sponsor, Vizuri Health Sciences, or its designee, will monitor the study. Study monitors representing the sponsor will visit study sites routinely throughout the trial. The sponsor/designee will review eCRFs and compare them with source documents to verify accurate and complete

collection of data and confirm that the study is being conducted according to the protocol. Auditors representing the sponsor may also similarly evaluate the study and its monitors.

A study coordinator at the study site will enter subject data into a remote data capture (RDC) database by completing eCRFs. All information recorded in the eCRFs for this study must be consistent with the investigator's source documentation for the study subjects. The study site will make available source documents to CTI personnel monitoring the study. The study monitor will verify consent of all subjects to participate in the study and will perform 100% source document verification of the eCRF data.

A CTI Clinical Data Associate (CDA) will review the data for discrepancies via programmed electronic consistency checks, data listings, or manually. Any discrepancies discovered via the data review process will be issued as queries in the RDC system to the study site for resolution. Once all the source verification is complete, all queries are resolved, and the database has been updated appropriately, the database will be locked and made available to CTI Biostatistics for final analyses.

All SAS programs used to create analysis datasets and output will be validated by ensuring that the ".log" files are void of all errors, warnings and notes indicative of problems. Additionally, each program will be checked to ensure that it performs according to the program specification. All programs are developed and validated by separate members of the CTI Biostatistics Department.

At the time of analysis, a quality control (QC) review of database values listed in SAS output will be compared to the database. The sample size of fields to undergo QC review will be determined by utilizing American National Standards Institute (ANSI) sampling procedures¹. Sampling procedures are conducted using "normal" inspection criteria (Inspection Level II, Single, and Normal) and an Acceptable Quality Level (AQL) of 0.010%. The following shows the sampling criteria:

Single Normal sampling procedure for Acceptable Quality Level (AQL) 0.010%

Number of Fields	Sample Size	Accept/Reject Criteria
2-8	2	0/1
9-15	3	0/1
16-25	5	0/1
26-50	8	0/1
51-90	13	0/1
91-150	20	0/1
151-280	32	0/1
281-500	50	0/1
501-1,200	80	0/1
1,201-3,200	125	0/1
3,201-10,000	200	0/1
10,001-35,000	315	0/1
35,001-150,000	500	0/1
150,001-500,000	800	0/1
500,001-up	1,250	0/1

4.2 Analysis Sets

The following three analysis sets will be defined for this study:

The intent-to-treat (ITT) set will be defined as all randomized subjects, whether or not they receive study drug.

The modified ITT (mITT) set will be defined as the subset of the ITT subjects that receive at least one dose of study medication and have at least one evaluable post-dosing efficacy endpoint. The mITT set will be defined based on randomized treatment rather than treatment actually received.

All efficacy analyses will be carried out using the mITT set.

The safety (SAF) set will be based on the ITT subjects who have received at least one dose of study medication (based on the treatment actually received rather than randomized treatment). All safety analyses will be carried out using the SAF set.

The Per Protocol (PP) set will include all mITT subjects in whom there were no major protocol deviations. Major protocol deviations for defining the PP analysis set will be identified by Vizuri prior to the database lock. If deemed appropriate, the analyses on primary and secondary efficacy endpoints listed in Section 6.1 and 6.2 will be repeated using the PP set.

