- c Application site pain will be assessed on NRS (0-10); application site erythema/edema will be assessed using modified categorical Draize test (0-3). Scaling and pruritus will also be scored on a similar categorical scale (0-3). Scoring for application site pain (not related to knee pain) will be performed on drug administration Days 1-4 (pre-application [≤30 min], and at 15 (± 5 min), 30 (± 5 min), 60 (± 5 min) and 90 minutes (± 5 min) after application) and on Days 5, 20, and 35. Application site skin reactions (erythema, edema, scaling, pruritus) will be assessed on drug administration Days 1-4 (pre-application [≤ 30 min], and at 15 (± 5 min), 30 (± 5 min), 60 (± 5 min) and 90 minutes (± 5 min) after application). (Appendix E and Appendix F).
- d OA knee pain to be scored on 100mm VAS scale pre-treatment (≤ 30 min) on Days 1-4.
- e WOMAC Pain, Stiffness, and Physical Function will be performed on Day 1 prior to drug administration (≤ 30 min).
- f Exploratory assessment of OA knee pain (average daily pain and daily worst pain) (pre-application [≤30 min]) (Appendix F).

"BASELINE" is defined in this study as the WOMAC scores (pain, stiffness, function) and the VAS OA knee pain score recorded within 30 minutes of the first application of study drug.

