6.5 ASSESSMENTS AT TIME OF SAE, EARLY TERMINATION OR UNSCHEDULED VISIT

Additional activities may be performed at the Investigator's discretion at the onset of an SAE, when subjects are prematurely taken off study, and/or for an unscheduled visit.

- Assess vital signs (BP, HR, RR, and T)
- Perform abbreviated symptom-driven physical exam (PE)
- Application site pain will be assessed on numerical pain rating scale (0-10);
 application site edema will be assessed using categorical Draize test (0-3).
 Scoring for application site pain (not related to knee pain) and for erythema and edema will be performed at Early Termination and at Unscheduled Visits.
- VAS OA knee pain and WOMAC will be performed at Early Termination and at Unscheduled Visits.
- Collect blood:

For local laboratory analysis:

- CBC with automated differential and platelets, and serum chemistry
- Document AEs and concomitant medications

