6. EFFICACY AND TOLERABILITY ANALYSES

All efficacy analyses will be carried out on mITT subjects. Tolerability analysis will be based on the safety analysis set. Only one knee will be indicated as the “Study Knee” for efficacy analyses. The Study Knee will be the knee with the highest WOMAC pain score at baseline. If both knees have equal WOMAC pain scores at baseline, then the right knee will be considered the Study Knee with regard to WOMAC pain and VAS pain score reduction. Data from both knees will be presented in the listings.

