6.2 Secondary Efficacy Endpoints and Analyses

Secondary efficacy endpoints will include: 1) the WOMAC pain scores at Day 5, 19, 64 and Day 94; 2) WOMAC scores on the stiffness and function subscales as well as total WOMAC score at Day 5, 19, 35, 64, and 94; 3) VAS OAKP assessments.

Data from WOMAC pain, stiffness, physical function subscales and total score, as well as VAS assessments will be listed and summarized by presenting descriptive statistics of raw data and change from baseline at each visit for each treatment group. Tabulation will be based on Study Knee and Non-study Knee.

WOMAC stiffness, function and total score reductions at Day 35 will be evaluated using the Study Knee. Change from baseline in WOMAC stiffness, function and total score on the Study Knee between each Active Treatment Arm and the Vehicle Arm at Day 35 will be evaluated using

ANCOVA model as described in Section 6.1.

The group mean reduction in OAKP score on a 100 mm VAS scale at Day 35 for each Active Treatment Arm will be compared to the Vehicle Arm using ANCOVA model as described previously.

For dose-response estimation, the difference of adjusted group mean between the 5% and the 1% Active Treatment Arms for the WOMAC pain, stiffness, function and total score at Days 35, 64 and 94 will be tested using the same method as described in Section 6.1.

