6.3 Clinical Response

Clinical response will be measured by reduction of WOMAC pain score on the Study Knee. In order for a subject to be considered to have successfully obtained a clinical response, the following criteria must be met: WOMAC pain score on the Study Knee reduced to 50% or less of baseline at any of the stated assessment times.

A subject with a missing WOMAC pain score on the Study Knee at a visit will be considered to have failed to achieve a clinical response for that visit.

The durability of clinical response up to Day 94 will be evaluated by a tabulation of clinical response at Days 19, 35, 64, and the Day 94 visit by treatment group. Subjects who have successfully met the above criteria (reduction of a least 50% in WOMAC pain score) at the Day 5 visit and who remain at least at this reduction of pain score or lower at the Days 19, 35, 64, and the Day 94 visit will be considered to have a durable clinical response through Day 94. Subjects who at no more than one of the post Day 5 visits have less than 50% reduction in WOMAC pain score will be considered to have a durable response through the last day at which reduction in WOMAC pain score is at least 50%. Patients who have less than 50% WOMAC pain score reduction on two or more of the post Day 5 visits will be considered to have failed to achieve a durable clinical response.

Each subject's clinical response status (Responder vs. Non-responder) at each visit and the durability of clinical response up to Day 94 will be summarized for each treatment group. Percent change from baseline in WOMAC pain score on both knees will be listed at each visit.

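### The missing-equals-failure rule for clinical response cannot reach dosed subjects with no post-dose efficacy score, because mITT has already removed them from the denominator

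*SAP*

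**What the plan says.** Three statements in the SAP combine to produce the effect.

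- **Who is analysed.** SAP 4.2 admits to mITT those randomised subjects who "receive at least one dose of study medication and have at least one evaluable post-dosing efficacy endpoint". It does not define an evaluable post-dosing efficacy endpoint.
- **Where the set applies.** SAP 6 opens with "All efficacy analyses will be carried out on mITT subjects". Clinical response and its durability (SAP 6.3) fall under that sentence. Protocol 9.3 and 9.5.3 also assign efficacy to mITT.
- **How a gap is scored.** SAP 6.3 states "A subject with a missing WOMAC pain score on the Study Knee at a visit will be considered to have failed" to respond at that visit.

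The output is a summary by arm: responder status "at each visit and the durability of clinical response up to Day 94 will be summarized for each treatment group". No test is specified. No responder summary on the ITT set or on all dosed subjects is planned, and the optional per-protocol repeat in SAP 4.2 covers only SAP 6.1 and 6.2.

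**The concern.** A non-responder rule lets a rate be computed over everyone treated without needing data from those who leave. Here the rule operates only after mITT has been formed, and mITT requires a post-dose score. A subject with one qualifying post-dose score who then disappears is a failure at every later visit. A subject who disappears before giving any score is not counted at all. The plan gives no reason for treating the two differently.

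Membership depends on what happens after randomisation, and that could differ by arm. Protocol 1.3 reports that, in the earlier vehicle-controlled study (VZU00023), burning-stinging pain occurred in 100% of subjects on 5% capsaicin and 35% on vehicle. Protocol 4.2 does not allow replacement of subjects who drop out for lack of tolerability, so such losses would not be made up. If they fell mainly in an active arm, that arm's response and durability rates would look better than they were among the subjects treated.

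**Working it through.** **The plan's own figure.** The only computed design figure is in SAP 9: 80% power for a difference of 63 with SD 100, 40 per arm and two-sided 5%. The standard error is 100 × √(2/40) = 22.36, and 63/22.36 = 2.817. Then 2.817 − 1.960 = 0.857, which gives 80.4% by the normal approximation (79.5% by the noncentral t). The figure reproduces, and this point does not affect it. No responder rate is stated anywhere in the plan.

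**Who is lost.** This depends on what counts as an evaluable post-dosing efficacy endpoint.

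- *If the VAS counts.* SAP 6.2 lists "3) VAS OAKP assessments" among the secondary efficacy endpoints, and the footnote to Protocol Table 6–2 has "OA knee pain to be scored on 100mm VAS scale pre-treatment" on Days 1 to 4. The first post-dose score is then the Day 2 pre-application VAS. Only subjects with no score from Day 2 onward, including at early termination, are lost.
- *If only the WOMAC counts.* The first scheduled post-dose WOMAC is Day 5. Anyone leaving during Days 1 to 4 without an early-termination WOMAC is lost.

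The gap exists on both readings and is wider on the second.

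**Effect on a rate.** Let r be the responders in an arm and k the dosed subjects with no qualifying post-dose score. Assume 40 dosed. Every responder has a score, so r is the same on either denominator.

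- All-dosed rate: r/40
- mITT rate: r/(40−k)
- Ratio of the two: 40/(40−k)

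Both r and k are assumptions:

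| k | 20 responders: all dosed | 20 responders: mITT | 32 responders: all dosed | 32 responders: mITT |
|---|---|---|---|---|
| 0 | 50.0% | 50.0% | 80.0% | 80.0% |
| 1 | 50.0% | 20/39 = 51.3% | 80.0% | 32/39 = 82.1% |
| 2 | 50.0% | 20/38 = 52.6% | 80.0% | 32/38 = 84.2% |
| 3 | 50.0% | 20/37 = 54.1% | 80.0% | 32/37 = 86.5% |
| 4 | 50.0% | 20/36 = 55.6% | 80.0% | 32/36 = 88.9% |

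**Effect on a difference between arms.** Assume 20/40 responders on active and 12/40 on vehicle, a 20.0-point difference among all dosed.

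- Four losses, all on active: 55.6 − 30.0 = 25.6 points.
- Four losses, all on vehicle: 12/36 = 33.3%, so 50.0 − 33.3 = 16.7 points.

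Within an arm a loss can only raise the rate. Between arms the direction depends on where the losses fall.

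**The case against.** **The rules do not conflict.** A reader might infer that SAP 4.2 and SAP 6.3 contradict each other. They do not. One defines who is analysed, the other how a missing visit is scored among those analysed, and both can be applied in full. The issue is the choice of denominator. Nor does the SAP give a reason for the non-responder rule, so no intent can be attributed to it.

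**Most early tolerability failures stay in.** A reader might also infer that the earliest tolerability failures as a group disappear from the rates. The documents do not support that. After treatment is stopped, "subjects should remain on study and will be followed for scheduled safety and study assessments through Day 35". Under Protocol 5.1.4 a subject who skips a dose should return for the next scheduled visit. Protocol 6.5 adds "VAS OA knee pain and WOMAC will be performed at Early Termination and at Unscheduled Visits", and Protocol Table 6–3 marks both for early termination. Anyone who gives a qualifying score is in mITT and is counted as a non-responder whenever later scores are missing. These safeguards are partial: subjects may withdraw at any time, and the sentence that opens Protocol 6.5 leaves the activities to the investigator's discretion.

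**Burning has not been shown to cause loss.** Protocol 1.3 reports no discontinuations for adverse events and no subject-requested withdrawals in either arm of VZU00023, despite the 100% against 35% contrast. A link between arm and loss is plausible but not demonstrated, and k may be zero.

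**Little rests on the summary.** Clinical response is not among the primary or secondary efficacy endpoints in SAP 2.2 or 6.2, no test is planned, and SAP 4.5 calls the study exploratory. Subjects outside mITT still appear in disposition, in the adverse-event tables and in the safety set.

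All four arguments limit the size and importance of the point. None shows that a dosed subject without a post-dose score is counted. SAP 4.4 (all dosed subjects included when appropriate) and Protocol 9.4 (all exposed subjects accounted for) do not override the mITT definition.

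**Conclusion.** The point holds as a minor one. Whenever a dosed subject has no evaluable post-dose efficacy score, the planned response and durability rates for that arm are too high by the factor 40/(40−k), relative to a rate over all 40 dosed. With an assumed 20 responders among 40, that is 1.3 points at k=1 and 5.6 points at k=4. With an assumed 32 responders, it is 2.1 and 8.9 points. It is nil at k=0, which the earlier studies suggest is possible. An active arm might be flattered, but the documents do not fix the direction of the between-arm effect. The primary ANCOVA, the power calculation and every planned p value are unaffected.

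**What to change.** In SAP 6.3, define the denominator for clinical response and durability as all randomised subjects who received at least one application, by randomised arm, with any missing WOMAC pain score counted as non-response, including for subjects with no post-dose score. Keep mITT for the ANCOVA. In SAP 4.2, say which assessments make a subject evaluable post-dose, and report by arm how many dosed subjects fall outside mITT and why.

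Protocol 9.3 and 9.5.3 also assign efficacy to mITT, so either align them or report the change as a deviation under Protocol 9.5.10. Do this before unblinding, so that the denominator is not chosen after results are known.

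The cost is a short SAP edit with a matching protocol note. No new data are needed. Response rates may be slightly less favourable, and a dosed subject who left for an unrelated reason before giving any score would also count as a non-responder.

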4.3 Assessment Windows

For the purpose of listing and summarizing data, the time-in-study for each subject observation will be defined using study days as defined in the Schedule of Events. No analysis windows are planned for the study regarding data collected outside the protocol specified windows. All data will be included in the analysis based on the visit as it is recorded in the database.

Baseline is defined as the last non-missing value prior to the first dosing.

If more than one assessment exists for a single visit, the value closest to the protocol study visit will be used for summary and analysis purposes. Data from all assessments will be listed.

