APPENDIX C SCHEDULE OF EVENTS

APPENDIX C: SCHEDULE OF EVENTS

Assessment	SCR	Treatment Days			Follow-up Period Days						
TIMEFRAME	Within 28 days of Day 1	D1	D2	D3	D4	D5 (Post Treat Day 1)	D19± 3d (Post Treat Week 2)	D35±3d (Post Treat Week 4)	D64± 3d (Post Treat Week 8)	D94± 3d (Post Treat Week 12)	Unscheduled, Early Termination, SAE ¹
Clinic visit	X	X	X	х	X	X	X	X	X	X	X
Informed Consent	X										
Inclusion / Exclusion	X										
Demographics	X										
Medical & Medication History	X										
Randomization		X									
Physical exam	x										X
Height and Weight ^a	X										
Vital Signs ^b	X	X	X	X	X	X				X	X
Knee X-rays ^c	X										
12-lead ECG ^d	X										
Clinical lab tests ^e	X					X		X		X	X
Pregnancy or FSH Test ^f	X	X									
Application Site Pain, Erythema, Scaling, Pruritus Assessment ^g	X	x	x	x	x	X	X	X	X	X	X
Exploratory Assessment of OA Knee Painh	X	X									
VAS OA Knee Pain Assessment ⁱ		X	X	X	X	x	X	X	X	X	X
WOMAC ^j	X	X				X	X	X	X	X	X
Drug administration		X	X	х	X						
Assess. Of Concomitant Medications ^k	X	X	X	X	X	X	X	X	X	X	X
AE Assessments		X	X	X	X	X	X	X	X	X	X
Study Exit										X	

Schedule of Events (Continued)

- a. Height and weight obtained at Screening.
- b. Vital signs include temperature, blood pressure, heart rate and respiratory rate. Performed at Screening, on Days 1-4 at pre-dose and at 90 minutes (± 5 min) after applying study drug to knees, and at Follow-up on Day 5 and 94.
- c. Knee X-rays of both knees must be obtained unless films/images performed within 6 months before screening. Copies of film and results will be requested.
- d. Standalone 12-lead ECG performed at Screening.
- e. Clinical laboratory tests include (Appendix A):

Hematology: full blood count including RBC, hemoglobin, hematocrit, MCV, MCH, MCHC, WBC, differential white cell count, platelet count (Screening, Day 5, Day 35 and Day 94);

Erythrocyte sedimentation rate (Screening only);

Chemistry: BUN, creatinine, uric acid, bilirubin (total), sodium, potassium, calcium, magnesium, phosphorous (inorganic), chloride, bicarbonate, ALK, AST (SGOT), ALT (SGPT), LDH, GGT, CPK, albumin, total protein, and glucose (Screening, Day 5, Day 35 and Day 94);

IgM RF (Screening only);

Urinalysis: pH, protein, glucose, ketones, bilirubin, blood, urobilinogen, specific gravity, leucocytes (Screening, Day 5, Day 35 and Day 94). Clinically significant abnormal dipstick results will require microscopic analysis.

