2.2 Endpoints

2.2.1 Primary Efficacy Endpoint

The primary efficacy endpoint of this study will be to examine the extent of reduction in the WOMAC pain score, relative to baseline, provided by once daily, one-hour application of Vehicle (CGS-200-0), CGS-200-1 and CGS-200-5 at the following assessment times:

Baseline: \leq 30 minutes prior to first daily application

Day 35: 31 Days (+/- 3 days) after fourth daily application

and based thereon to determine whether the responses for treatment with CGS-200-1, and CGS-200-5 are significantly different from Vehicle (CGS-200-0) and from each other at the primary endpoint time.

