6.1 Primary Efficacy Endpoint and Analysis

The primary efficacy endpoint is the change from baseline in WOMAC pain score at Day 35. WOMAC pain score reduction at Day 35 will be evaluated using the “Study Knee”.

Change from baseline in WOMAC pain score on the Study Knee between each Active Treatment Arm and the Vehicle Arm at Day 35 will be evaluated using analysis of covariance (ANCOVA) model. The ANCOVA model will be fitted with the treatment as a fixed effect, baseline value as a covariate and treatment-by-baseline interaction. The adjusted group mean (least squares mean) changes will be compared at a 2-sided significance level of 0.05. The *p* value along with the 95% confidence interval for the treatment difference will be reported.

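### SAP 4.3 assigns WOMAC by visit label alone, so a score taken on Days 32-38 but recorded as early termination or unscheduled cannot reach the Day 35 analysis, while an off-window score labelled Day 35 can

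*SAP*

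**What the plan says.** The SAP fixes the time of the primary endpoint in section 2.2.1 as "31 Days (+/- 3 days) after fourth daily application", and section 6.1 carries it into the analysis: "The primary efficacy endpoint is the change from baseline in WOMAC pain score at Day 35".

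Section 4.3 then sets how a score is tied to a visit. It says "No analysis windows are planned for the study regarding data collected outside the protocol specified windows", followed by "All data will be included in the analysis based on the visit as it is recorded in the database". Dates matter in one situation only: "If more than one assessment exists for a single visit, the value closest to the protocol study visit will be used".

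Protocol 6.5 adds a second source of scores: "VAS OA knee pain and WOMAC will be performed at Early Termination and at Unscheduled Visits". In the Schedule of Events (Protocol Appendix C) these assessments have their own column, headed "Unscheduled, Early Termination" and so on, apart from the Day 35 column.

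SAP 4.4 leaves missing values missing, apart from item-level imputation within a WOMAC subscale. For the responder summary, SAP 6.3 goes further: "A subject with a missing WOMAC pain score on the Study Knee at a visit will be considered to have failed" to respond at that visit.

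**The concern.** The endpoint is defined by time since treatment, but nothing in the analysis enforces that time. Two things can go wrong.

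- **A valid score is not used.** WOMAC may be measured inside the endpoint's own window and filed under a label that the Day 35 analysis does not read. The ANCOVA loses the value, and the responder summary replaces a measured score with an assumed failure.
- **An off-window score is used.** A visit labelled Day 35 but held much later is analysed as Day 35. The trial asks whether relief persists about one month after four applications, and the SAP treats Days 64 and 94 as separate time points. A late score mixes a different duration into the primary contrast.

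In both cases the result depends partly on how a site labels a visit, so the same data could give different Day 35 results.

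**Working it through.** **1. The window.** The fourth application is on Day 4, and 4 + 31 = 35. With +/- 3 days, the window is Days 32-38.

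**2. An in-window score under another label.** Take a subject whose last WOMAC is on Day 33 and is recorded as early termination.
- SAP 4.3 assigns it by label, so it is not a Day 35 score.
- The closest-value rule chooses among records within one visit. It cannot move a score from one label to another.
- SAP 4.4 leaves the Day 35 value missing, so the subject contributes nothing to the ANCOVA in SAP 6.1.
- SAP 6.3 counts the subject as a Day 35 failure whatever the Day 33 score shows.

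There is a plausible route to this. Protocol 6.10 follows subjects who permanently stop treatment through Day 35, whereas study exit is Day 94. A last visit can therefore fall in the primary window and be recorded as an early termination.

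Durability is less exposed. If missing visits count as failures there too, this subject also fails at Days 64 and 94. Two failures already rule out a durable response, so recovering Day 35 would not change that classification.

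**3. An off-window score under the Day 35 label.** Take a visit labelled Day 35 and held on Day 55. It is 55 - 38 = 17 days past the window, 20 days from Day 35 and 9 days from Day 64. SAP 4.3 analyses it as Day 35.

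**4. The plan's own power figure.** SAP section 9 gives 80% power for n = 40 per arm, difference 63, SD 100, two-sided 5%.
- Normal approximation: 63 / (100 x sqrt(2/40)) = 2.817; 2.817 - 1.960 = 0.857; power = 80.4%.
- Two-sample t-test: 79.5%.

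The figure reproduces.

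**5. Size, under assumed counts.** The documents give no rate, so these are ranges and not forecasts. All use the t-test with difference 63 and SD 100, without baseline adjustment.

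| Values lost per arm | n analysed per arm | Power | Largest fall in an arm's Day 35 responder rate (lost / 40) |
|---|---|---|---|
| 0 | 40 | 79.5% | 0 |
| 1 | 39 | 78.4% | 2.5 points |
| 2 | 38 | 77.3% | 5 points |
| 4 | 36 | 75.1% | 10 points |

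The last column is reached only if every lost subject had in fact responded.

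For off-window scores, let a share f carry r times the treatment effect. The difference becomes 63 x (1 - f + f x r), with n = 40 per arm:

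| f | r = 0.5: difference, power | r = 1.5: difference, power |
|---|---|---|
| 5% | 61.4, 77.4% | 64.6, 81.4% |
| 10% | 59.9, 75.3% | 66.2, 83.2% |
| 20% | 56.7, 70.7% | 69.3, 86.5% |

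The effect can go either way.

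**The case against.** **The early-termination label is inferred.** No text says that a Day 33 departure must be recorded that way. A site could enter it as Day 35, since it lies inside that visit's window, and SAP 4.3 opens by referring to study days in the Schedule of Events. The SAP's only explicit exclusion of unscheduled visits concerns vital signs (section 7.4). This stands, and it limits the point to scores that do carry another label. It also shows that the outcome rests on site practice, which an SAP should not leave open.

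**Other provisions deal with off-window visits.** Deviations are tabulated and listed (SAP 5.2), a per-protocol analysis may be run (SAP 4.2), and the sponsor may exclude individual values (Protocol 9.5.9). Listing a deviation does not change the analysis, and the other two are discretionary. None brings an unmapped score back.

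**The number is probably small.** Dosing ends on Day 4, treatment stoppers are followed through Day 35, dropouts before that visit may be replaced, and Protocol 1.3 reports no discontinuations for adverse events in VZU00021 or VZU00023. SAP 4.5 also calls the trial exploratory. All of this stands and keeps the point modest. The allowance of up to 10 replacements per arm is a ceiling for any incomplete dosing or dropout before Day 35, so it should not be read as a rate of in-window departures.

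**Reassigning every score by date has its own costs.** A late Day 35 score could become missing and then a failure in SAP 6.3. An unscheduled score prompted by an event could displace a scheduled one, although Protocol 6.8 ties the return to baseline analgesic doses to clinical assessment visits. This stands, and it is why the fix leaves scheduled visits on their labels.

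**Conclusion.** The point holds as a gap in the visit-assignment rule. As written, a WOMAC score taken on Days 32-38 but recorded as early termination or unscheduled has no route into the Day 35 analysis, and a score labelled Day 35 is used however late it was taken.

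A reader might infer that such subjects count as non-responders in the primary analysis. They do not: the primary ANCOVA treats them as missing, and the failure rule belongs to SAP 6.3 alone. A reader might also infer that the plan expressly discards early-termination WOMAC. It does not say so, and such a score could still help qualify a subject for the mITT set. The gap comes from label-based assignment with no mapping rule.

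The number affected is unknown and probably small, and the direction of bias is not fixed. Under the assumed losses of one to four values per arm, power falls by about 1 to 4 points, and an arm's Day 35 responder rate by at most 2.5 to 10 points. The case for change is that the scores and dates are already collected. It does not rest on a demonstrated threat to the primary result.

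**What to change.** Amend SAP 4.3 before unblinding:

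1. Where no score is recorded under a scheduled visit label, use an early-termination or unscheduled WOMAC or VAS score whose actual study day falls in that visit's protocol window (Day 35 +/- 3, and likewise Days 19, 64 and 94). If there are several, take the one closest to the target day.
2. Apply this in both the ANCOVA and the SAP 6.3 responder analysis.
3. A scheduled-visit score always takes precedence, and scheduled visits stay assigned by label in the primary analysis.
4. Prespecify a sensitivity ANCOVA limited to Day 35 scores actually taken on Days 32-38.

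The cost is a short SAP amendment, one derived variable from dates already collected, and one extra analysis. The drawback is that a few of the unscheduled scores brought in may have been prompted by an event. Because they are used only when no scheduled score exists, this exposure is limited.
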